1.1 Study design

This is a randomized, Phase III, open-label, active-controlled, multi-center study comparing safety and efficacy of asciminib to bosutinib in patients with CML-CP, previously treated with 2 or more tyrosine kinase inhibitors (Figure 1-1). Approximately 220 patients will be randomized to one of the following treatment arms in 2:1 ratio:

- asciminib 40 mg BID
- Bosutinib 500 mg QD

Randomization will be stratified by the following factor: cytogenetic response status (with or without major cytogenetic response).

Figure 1-1 Schematic of Study Design

Patients with documented treatment failure (as per the 2013 ELN guidelines, [Baccarani et al 2013](#)) while on bosutinib treatment will have the option to switch to asciminib treatment within

96 weeks after the last patient has been randomized on study. The patients who switch to asciminib will be able to receive asciminib up to the end of study treatment (EOsT) period.

Patients will be treated up to the EOsT defined as up to 96 weeks after the last patient received the first study dose (LPFT) or up to 48 weeks after the last patient has switched to asciminib treatment whichever is longer, if they do not discontinue study treatment earlier. After the EOsT, the assigned study treatment will be made available to patients who in the opinion of the investigators are still deriving clinical benefit. This may be outside of this study through alternative options including, but not limited to, an expanded access/compassionate use/managed access program or access to commercial supplies in applicable countries.

Major Molecular Response (MMR) rate at 24 weeks is the primary endpoint in this study. MMR rate at 96 weeks is the key secondary endpoint.

Four analyses are planned for this study, including the 24-week primary analysis, the 96-week analysis, the End-of-Study-Treatment (EOsT) analysis, and Progression-Free survival/Overall survival (PFS/OS) update analysis. The timing when those analyses are conducted is summarized in Section 2.1.

No formal interim efficacy analysis is planned in this study. A data monitoring committee (DMC) will monitor unblinded safety data approximately 6 months after the first randomized patient has started study treatment. Subsequent reviews will be conducted approximately every 6 months and when needed thereafter (ie. if significant safety findings are noted) until the primary analysis.

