2.1 Data analysis general information

The planned analyses will be performed by Novartis and/or a designated CRO. SAS version 9.4 or later will be used to perform all data analyses and to generate tables, figures and listings.

There is no planned interim efficacy analysis. Prior to the database lock for the primary analysis, tables and figures aggregated by treatment arm for safety data review by the data monitoring committee or for other reporting activities will be produced by an independent statistician and independent statistical programmers.

For between-treatment comparisons of efficacy endpoints, randomization stratification factor, i.e. cytogenetic response status (MCyR vs no MCyR) at screening, will be included in respective stratified statistical tests.

Data included in the analyses

The analysis data cut-off dates for the planned analyses are:

- Primary analysis: After all randomized patients have been on study treatment for 24 weeks or discontinued earlier, i.e., LPFT + 24 weeks.
- 96-week analysis: After all randomized patients have been on study treatment for 96 weeks or discontinued earlier, i.e., LPFT + 96 weeks
- End of study treatment analysis: 30 days after the EOSt. (Note: After the study treatment period, the assigned study treatment will be made available, may be outside of this study, to patients who in the opinion of the investigators are still deriving clinical benefit.)
- PFS/OS update analysis: 5 years from the date when the last randomized patient received the first study dose (irrespective of treatment switch for patients failing bosutinib).

All statistical analyses will be performed using all data collected in the database up to the respective data cut-off date. All data with an assessment date or event start date (e.g. vital sign assessment date or start date of an adverse event) prior to or on the cut-off date will be included in the analysis. Any data collected beyond the cut-off date will not be included in the analysis and will not be used for any derivations.

All events with start date before or on the respective cut-off date and end date after the respective cut-off date will be reported as ongoing. The same rule will be applied to events starting before or on the respective cut-off date and not having documented end date. This approach applies, in particular, to adverse event and concomitant medication reports. For these events, the end date will not be imputed and therefore will not appear in the listings.

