2.1.1 General definitions

Investigational drug and study treatment

Investigational drug, will refer to the asciminib only. Whereas, *study treatment* will refer to asciminib or control treatment, i.e. bosutinib, received during the treatment phase. Switched treatment will refer to asciminib received during treatment switch phase.

Treatment arms

- Asciminib (Subjects randomized to asciminib arm at the beginning of the study)
- Bosutinib (Subjects randomized to bosutinib arm at the beginning of the study)

Date of end of study treatment (EOsT)

The EOsT date is the date that the study treatment is ended for the entire study. On this date, patients are treated for at least 96 weeks if they are not eligible to switch study treatment or are treated for at least 48 weeks after they have switched to asciminib treatment, unless patients have discontinued study treatment earlier

Date of first administration of randomized study treatment

The date of first administration of randomized study treatment (FD) is derived as the first date when a non-zero dose of study treatment was administered as per the Dosage Administration Record (DAR) electronic case report form (eCRF). The date of first administration of study treatment will also be referred as *start of study treatment*.

The date of first administration of randomized study treatment is the same as the date of first administration of investigational drug or control drug.

Date of first administration of switched treatment

For subjects switching from bosutinib to asciminib, the date of first administration of switched treatment (FD_{switch}) is derived as the first date when a non-zero dose of asciminib was administered as per the DAR eCRF. The date of first administration of switched treatment (asciminib) will also be referred as *start of switched treatment*.

Date of last administration of randomized study treatment

The date of last administration of randomized study treatment (LD) is defined as the last date when a non-zero dose of study treatment was administered as per DAR eCRF. For subjects switching from bosutinib to asciminib, this includes the dose of bosutinib administered as bridging therapy between their treatment failure and the first dose of asciminib administered.

The date of last administration of randomized study treatment is the same as the date of last administration of investigational drug or control drug.

Date of last administration of switched treatment

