2.7.3 Handling of missing values/censoring/discontinuations

MMR rates at specific time points: Patients discontinuing the randomized treatment prior to a specific time point due to any reason or patients without an available assessment at that time point will be considered as non-responders for that time point.

MMR rates by specific time points:

Patients without any documented response for which an evaluable response assessment was never provided will be considered as non-responders for the period of time up to that time point.

Molecular response at specific time points: The category “Missing” will be assigned to

- Ongoing cases, i.e. patients without assessment at the specific time point who have not discontinued study treatment and have not been treated sufficiently long for a specific time point
- Discontinued due to progressive disease/death prior to a specific time point
- Discontinued due to other reasons prior to a specific time point
- **Molecular response category by specific time points:** The category “Missing” will be assigned to patients for whom an evaluable response assessment was never provided.

Time to MMR: For patients in the FAS who have not experienced any MMR, the time will be censored as follows in the Kaplan-Meier analysis:

- If a patient does not achieve the specified response before the cut-off date for the analysis, censoring time will be the last molecular assessment (PCR) date on treatment prior to the cut-off date or the EoT visit, whichever comes first.
- If a patient discontinues study treatment prior to achieving a response for a reason other than disease progression or death, then the patient will be censored at the last molecular assessment (PCR) date on treatment prior to the cut-off date or the EoT visit, whichever comes first.
- If a patient discontinues study treatment prior to achieving a response due to progression or death, then the censoring time will be set to the longest follow-up time in the treatment group, that is, consider the response is impossible to reach.
- In case no on-treatment response assessment was performed, the patient will be censored at day 1.

Duration of MMR: For patients in the MMR responder set who have not experienced any event (loss of MMR, progression to AP/BC, or CML-related death), the duration will be censored at the last molecular assessment (PCR) date on treatment.

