To assess the impact of mistratifications on the treatment effect assessment, the same analysis will be repeated, adjusting for major cytogenetic status at baseline based on CRF data instead of based on randomization data.

Influence of early molecular response levels on long term molecular response levels

The relationship between MMR status at 24 weeks and MMR status at 48 and 96 weeks will be explored using FAS by reporting contingency tables and by applying a logistic regression including treatment group, MMR status at 24 weeks and their interaction as covariates. Treatment group will be included in this summary table. The odds ratios between treatment groups with 95% confidence intervals will be reported, for each category of MMR status at 24 weeks and overall. If the interaction of treatment by MMR status at 24 weeks is significant (e.g. when $p < 0.1$), overall odds ratio for treatment will not be reported.

Efficacy Analysis on Switch Analysis Set

Efficacy analyses on the Switch Analysis Set will be performed at the time of the 96-week analysis. Unless otherwise specified, endpoints are defined and analyzed similarly as specified in Sections 2.5, 2.6, and 2.7 on Switch Analysis Set, but with baseline, FD, LD, and EoT replaced by baseline_switch, FD_{switch}, LD_{switch}, and S-EoT. The below are the efficacy endpoints to be analyzed:

- MMR rate at and by all protocol-planned visits.
- CCyR rate at and by all protocol-planned visits.
- Time to MMR
- Duration of MMR
- Time to CCyR
- Duration of CCyR
- Time to Treatment Failure

The analysis of time-to-event endpoints will be conducted only if at least 5 events are observed.

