5.4.2 Cytogenetic response

Cytogenetic response will be based on the percentage of Ph⁺ metaphases in the bone marrow. Cytogenetic evaluations will be considered for response assessment only if the number of metaphases examined is ≥ 20 in each bone marrow sample. As per protocol, fluorescent *in-situ* hybridization (FISH) assessments will not be considered for any evaluation of cytogenetic response during treatment.

Cytogenetic response is categorized as follows (a review of a minimum of 20 metaphases is required):

- Complete response (CCyR): 0% Philadelphia chromosome positive (Ph⁺) metaphases
- Partial response (PCyR): >0 to 35% Ph⁺ metaphases
- Major response (MCyR = CCyR + PCyR): 0 to 35% Ph⁺ metaphases
- Minor response (mCyR): >35 to 65% Ph⁺ metaphases
- Minimal response: >65 to 95% Ph⁺ metaphases
- None: >95 to 100% Ph⁺ metaphases.

If bone marrow aspirate blast percentage is provided as ‘ $<X$ ’ (i.e. below limit of detection), the numeric value is set to X for summary tables. In the listing ‘ $<X$ ’ will be presented.

Complete cytogenetic response (CCyR)

CCyR is defined as a value of 0% Ph⁺ metaphases in bone marrow.

CCyR will be considered as a binary variable with patients achieving CCyR grouped as ‘responders’ and patients not achieving CCyR, patients with missing cytogenetic evaluations grouped as ‘non-responders’.

Loss of CCyR

Loss of CCyR is defined as an increase in the Ph+ bone marrow cells to > 0%.

Loss of CCyR must have led to treatment discontinuation because of lack of efficacy (based on the “End of Treatment Phase Disposition” eCRF or “End of Treatment Disposition” eCRF during the Treatment switch phase with Subject status=“lack of efficacy” and Reason of treatment failure = “After start of therapy, loss of CHR, CCyR or PCyR”).

In addition, CML-related death or progression to AP or BC will be considered as loss of CCyR in any case (if they occurred on treatment).

Major cytogenetic response (MCyR)

MCyR is defined as a value of 0% to 35% Ph+ metaphases in bone marrow.

MCyR will be considered as a binary variable with patients achieving MCyR grouped as ‘responders’ and patients not achieving MCyR, patients with missing cytogenetic evaluations grouped as ‘non-responders’.

Loss of MCyR is defined as an increase in the Ph+ bone marrow cells to > 35%. For patients with response = PCyR, this would constitute loss of PCyR.

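### Switch Analysis Set: a post-switch visit not yet reached at the 96-week cut-off counts as non-response, so the exploratory MMR and CCyR rates by visit are understated when patients switch late

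*Combined protocol and SAP*

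**What the plan says.** The section numbers below refer to the SAP with addendum 1.0 (14 October 2020), the latest full text available.

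- **Timing of the analysis.** Section 2.14: "Efficacy analyses on the Switch Analysis Set will be performed at the time of the 96-week analysis". Section 2.1 sets that cut-off: "96-week analysis: After all randomized patients have been on study treatment for 96 weeks or discontinued earlier, i.e., LPFT + 96 weeks". It also closes the data there: "Any data collected beyond the cut-off date will not be included in the analysis and will not be used for any derivations".
- **Last date for switching.** Section 1.1 lets a bosutinib patient with documented failure switch within "96 weeks after the last patient has been randomized on study".
- **Missing visits.** Section 2.7.3, on MMR rates at a time point: "patients without an available assessment at that time point will be considered as non-responders for that time point". Section 5.4.1 treats missing PCR evaluations the same way. For CCyR, Section 5.4.2 has "patients with missing cytogenetic evaluations grouped as" non-responders.
- **How these rules reach the switch set.** Section 2.14 applies Sections 2.5 to 2.7, "but with baseline, FD, LD, and EoT replaced by baseline_switch, FD_{switch}, LD_{switch}, and S-EoT". The date of randomization is not in that list.
- **End of study treatment (EOsT).** Section 2.1.1 defines EOsT so that switchers still on treatment are "treated for at least 48 weeks after they have switched to asciminib treatment". Section 2.15 describes an EOsT analysis, to be done if required and possibly together with the 96-week analysis.

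**The concern.** The visit clock restarts at the first switched asciminib dose, but the data stop at a date set by the start of randomized treatment. A patient who switched ten weeks before the cut-off is still on asciminib and has not come to post-switch Week 24 (S-Week 24), yet enters that visit's rate as a failure. This is administrative truncation and says nothing about response. It can only push the at-visit rates down. The by-visit (cumulative) rates are affected less, because a patient who responded early still counts.

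The switch set is this trial's source of efficacy data for asciminib after bosutinib failure, and readers will take these percentages as the drug's activity in that setting.

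**Working it through.** **1. The plan's own figures.** The SAP gives no sample size or expected rate for the switch set. Its upper bound is the bosutinib arm. Section 3.1 (15% versus 35%, two-sided 5%, 90% power, 2:1) reproduces as 74 + 148 = 222 with pooled variance and no continuity correction. The set therefore has at most about 74 patients.

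**2. Shortest post-switch follow-up at the cut-off.** The last permitted switch is at last randomization + 96 weeks, and the cut-off is at last first dose (LPFT) + 96 weeks. They differ only by the lag between those two starting dates, so follow-up can be close to zero.

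**3. Follow-up needed for a PCR value.** Table 2-1 applies with Day 1 at the first switched dose. The Week 24 window opens on Day 142; from Week 36 on, windows open on Day 7k − 40.

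| Visit | Window opens | Days after switch | Weeks | Latest switch for a patient first dosed at LPFT |
|---|---|---|---|---|
| S-Week 24 | Day 142 | 141 | 20.1 | Week 75.9 |
| S-Week 48 | Day 296 | 295 | 42.1 | Week 53.9 |
| S-Week 96 | Day 632 | 631 | 90.1 | Week 5.9 |

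The last column is 96 minus the weeks. The cytogenetic windows in Table 2-2 open earlier (Day 2 for Week 24, Day 254 for Week 48), so the sizes below are for MMR. For CCyR the direction is the same.

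**4. Dilution.** Let f be the share of switchers whose time from switch to cut-off is too short for a value. If late switchers would respond as often as the others, reported rate = true rate × (1 − f).

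Assume switches spread evenly over 150 weeks and a true rate of 25% (neither is in the documents):
- S-Week 24: f = 20.14/150 = 13.4%; 25% × (1 − 0.1343) = 21.6%.
- S-Week 48: f = 42.14/150 = 28.1%; 25% × (1 − 0.2810) = 18.0%.

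**5. Other assumed patterns.** Simulations used uniform accrual over 78 to 130 weeks. Switch times were either uniform from week 24 to the cut-off, or exponential with mean 26 to 52 weeks starting at week 12 to 24.

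| Visit | Switchers able to have a value | Relative understatement |
|---|---|---|
| S-Week 24 | 81–99% | about 1–19% |
| S-Week 48 | 60–95% | about 5–40% |
| S-Week 96 | 18–67% | about 33–82% |

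**6. Does an existing provision correct it?**
- *Adequate-follow-up denominator (Section 2.7.2, post hoc).* It admits a subject when the time from randomization to cut-off reaches the time point. Every switcher was randomized no later than his or her first bosutinib dose, which was no later than LPFT. All are therefore at least 96 weeks from randomization at the cut-off, and the rule as worded removes no switcher for any visit up to S-Week 96. It also covers MMR only.
- *EOsT.* EOsT is the later of LPFT + 96 weeks and last switch + 48 weeks. If the last switch is by LPFT + 48 weeks, the two cut-offs nearly coincide and every switcher already has 48 weeks of potential follow-up. If it is later, EOsT comes after the 96-week cut-off and supplies the 48 weeks. In both cases visits after S-Week 48 can remain diluted.

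**The case against.** The strongest reply is that the EOsT analysis already answers the point. Section 1.1 counts it among four planned analyses, Section 2.1 gives it its own cut-off, and Section 2.15 makes its content similar to the 96-week analysis. Being done only if required has a natural meaning: a separate analysis is needed exactly when someone switches after LPFT + 48 weeks. This is a sensible reading and lowers the weight of the concern. But the SAP does not state that link, does not say that the switch-set efficacy tables are repeated, and Section 2.14 names only the 96-week analysis.

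A second reply is that Section 2.14 asks for endpoints to be analysed similarly, so a careful programmer would move the adequate-follow-up rule to the switch date. That is possible, but the replacement list omits randomization, and there is no such rule for CCyR.

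A third is that not every display is affected. Kaplan-Meier time to MMR and to CCyR censors patients still on treatment without a response (Section 2.7.3), and response-category tables show those not yet treated long enough as Missing. This stands. However, Section 2.14 runs time-to-event analyses only with at least 5 events, and its list of switch endpoints names the rates but not the category tables.

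Finally, the set is small and untested. With all 74 patients and a 25% rate, the 95% half-width is 1.96 × √(0.25 × 0.75/74) = 9.9 points, against an illustrative loss of 25 − 21.6 = 3.4 points at S-Week 24. This also stands and keeps the point minor. Protocol Section 10.6.1.1, amended for the switch measure, is in a part not available here and may address timing or denominators.

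**Conclusion.** The concern holds for the MMR and CCyR rates at each post-switch visit, and more weakly for the by-visit rates, in the exploratory Switch Analysis Set at the 96-week cut-off. The direction follows from the SAP's own rules. The size does not: it depends on switch times that the documents do not give. On the even-150-week assumption, a true 25% MMR rate would be reported as about 21.6% at S-Week 24 and 18.0% at S-Week 48. If most patients switch early, the loss at S-Week 24 may be about 1% in relative terms. If nobody switches after LPFT + 48 weeks, there is none from this source through S-Week 48.

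Three stronger readings might be inferred, and the documents do not support them:
- That all post-switch efficacy is understated. Kaplan-Meier time to response and the Missing category tables do not share the bias.
- That 24/150 = 16% and 48/150 = 32% of switchers lack a value on the same assumption. The windows accept a sample from Day 142 and Day 296, so patients past those days can have one.
- That the main results are at risk. The primary and key secondary analyses do not use post-switch data, and no test is made on the switch set.

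Severity is minor.

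**What to change.** Add two statements to SAP Section 2.14.

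1. At every cut-off, both 96-week and EOsT, the denominator for the MMR and CCyR rate at or by an S-visit is the switch-set patients whose time from first switched asciminib dose to the cut-off reaches that visit, regardless of earlier discontinuation. Patients who discontinued early thus stay in as non-responders, and only those whose visit lies beyond the cut-off drop out. This is the Section 2.7.2 rule with a new starting date, extended to CCyR. It is needed at EOsT too, because visits after S-Week 48 can remain incomplete there.
2. The switch-set efficacy tables are repeated at the EOsT analysis whenever EOsT falls after LPFT + 96 weeks.

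The 96-week display can stay, with the number of patients contributing shown at each visit. The cost is SAP wording and some programming, with no new data. The downsides are smaller denominators at late S-visits and final switch results that wait for EOsT.

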2.15 Interim analysis

No formal interim analysis is planned for this trial.

Three to four analyses are planned with the analysis data cut-off dates and the scope of analyses as follows:

- **24-week Primary analysis:** Formal testing of the primary endpoint with full alpha will be performed. Analyses of other efficacy endpoints at and by 24 weeks will also be performed.
- **96-week analysis:** Formal statistical testing of the key secondary endpoint will be performed with $\alpha = 0.05$ (two-sided) only if the primary endpoint (i.e. MMR rate at 24 weeks) is significant. Otherwise, no statistical testing will be performed, and any analysis will be considered exploratory. Analyses of other efficacy endpoints will also be performed.
- **End of study treatment (EOsT) analysis (if required):** similar to the 96-week analysis without formal statistical testing.

NOTE: This analysis may be conducted at the same time as 96-week analysis.

- **5-year PFS/OS update analysis:** PFS and OS.

In addition, DMC safety analyses will be conducted. Prior to the database lock for the primary analysis, tables and figures aggregated by treatment arm for safety data review by the DMC or for other reporting activities will be produced by an independent statistician and independent statistical programmers.

3 Sample size calculation

